10.2.2. Hepatitis and HIV Tests

Test for Hepatitis B, C and human immunodeficiency virus (HIV) viral load will be performed for each subject at Screening Visit. The results will be listed only.

10.2.3. Vital Signs

Vital signs will be evaluated for each subject at scheduled visits for systolic and diastolic blood pressure (SBP and DBP, mmHg), pulse rate (beats per minute [bpm]), respiratory rate (RR, breaths per minute [bpm]), and oral temperature (Fahrenheit °F).

Observed values and the change from Baseline (Day 1) at each visit will be summarized using descriptive statistics. Temperatures in Celsius (°C) will be reported for the summary. Fahrenheit to Celsius conversion $^{\circ}\text{C} = (^{\circ}\text{F} - 32) \times 5/9$ will be used.

10.2.4. Physical Exam

Physical exam will be performed for each subject at scheduled visits. Number and percentage of subjects in each body site system of Normal/Abnormal (Non-Clinically Significant [NCS] or Clinically Significant [CS] determinate by the investigator) category will be summarized. The

percentages of Normal/Abnormal results will be calculated based on the actual number of subjects at each visit in each treatment group of the SAS.

Abnormality changes from Baseline (Day 1) in terms of NCS or CS at each post-baseline visit will be summarized in the categories of (New, Unchanged, Worsened, or Improved). New is defined as an abnormal result in the post-baseline visit compare to the normal result at baseline. Unchanged is defined as the same abnormal result in both the post-baseline visit and the baseline. Worsened is defined as an abnormal CS result in the post-baseline visit compare to the abnormal NCS result at baseline. Improved is defined as an abnormal NCS result in the post-baseline visit compare to the abnormal CS result at baseline or a normal result in the post-baseline visit compare to the abnormal (NCS or CS) result at baseline.

10.3. Immunogenicity Analyses

Serum will be analyzed for the presence of anti-RSLV 132 antibodies using a validated immunoassay. Each positive serum sample will be evaluated for anti-drug antibodies (ADA) specificity by repeating the immunoassay in the presence of an excess of RSLV-132. Confirmed positive, specific serum samples will be titered by serial dilution and a numerical titer will be assigned. The immunogenicity of RSLV-132 as measured by the presence of RSLV-132 antibodies will be evaluated as part of the safety endpoints.

The serum samples for evaluating ADA will be collected for each subject at scheduled visits. To assess immunogenicity, the number and percent of positive and negative results will be summarized descriptively by treatment groups on the SAS. The percentages will be calculated based on the number of subjects in each treatment group with samples available at each visit.

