### **3.4.1 Study 132-01 – Single Ascending Dose Study Summary:**

This first-in-man study was a double-blind, placebo-controlled study conducted in healthy volunteers in a phase one unit to assess the safety and tolerability of a single, escalating IV dose of RSLV-132 (0.3 mg/kg – 10.0 mg/kg). There were no SAEs, or drug discontinuations due to an AE. The drug was well tolerated at all doses tested and an MTD was not reached. The serum half-life of the drug was measured to be approximately 16 days. None of the subjects in the study were positive for anti RSLV-132 antibodies.

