## **5 INVESTIGATIONAL PLAN**

### **5.1 Overall Study Design and Plan**

This is a multi-center, double-blind, placebo-controlled study of approximately fifty subjects with SLE. Potential subjects will be screened to assess their eligibility to enter the study within twenty-eight days prior to study entry (i.e., prior to Baseline visit).

Subjects will be evaluated during screening for evidence of active, evaluable cutaneous manifestations of SLE which will be measured by the investigator using the CLASI score and documented using photography. The photographs will be adjudicated by a dermatologist with expertise in the use of the CLASI tool in SLE clinical trials in order to confirm the subject meets the CLASI entry criteria.

Following Baseline evaluations on Day 1, subjects will receive their first intravenous infusion of RSLV-132. Subjects will return to the research unit for additional visits as described in Appendix A.

The subjects will be randomized 2:1 (active:placebo) to receive IV administrations of 10 mg/kg of study drug or placebo as follows on days:

- 1, 8, 15, 29, 43, 57, 71, 85, 99, 113, 127, 141, and 155

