### 12.3 Baseline (Day 1) Procedures

Prior to study drug administration (pre-dose procedures):

- the inclusion/exclusion criteria will be re-evaluated (CLASI score and concomitant medications only);
- directed physical examination;
- pregnancy test (urine);
- AE Assessment;
- interim medical/medication history;
- vital signs (temperature, respiratory rate, blood pressure and pulse);
- clinical laboratory evaluations (Chem-20, CBC, and UA);
- measurement of SLE disease activity (CLASI, SLEDAI-2K, BILAG-2004, PGA);
- tender and swollen joint count
- photographs of cutaneous SLE lesions;
- FACIT Index (subject completes form);
- serum sample for study drug concentration;
- serum for protein analysis;
- serum sample for measurement of RNase activity;
- whole blood for gene expression profile;
- serum sample for autoantibody profile (Ro-52/60, La, Sm, SmRNP, U1 RNP A/68, dsDNA) C3 and C4 (local or central laboratory);
- serum for assessment of antibodies to RSLV-132;
- **after completion of above assessments:**
  - study drug administration

### 12.4 Procedures on Days 8, 15, 43, 71, 99, 127, and 155

Prior to study drug administration (pre-dose procedures):

- adverse event assessment;
- interim medication history;
- vital signs (temperature, respiratory rate, blood pressure and pulse);
- serum for assessment of anti-RSLV-132 antibodies (Day 15 only)
- measurement of cutaneous disease activity (CLASI) – (Days 99, 127 and 155 only);
- **after completion of above assessments:**
  - study drug administration

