### 12.5 Procedures on Days 29, 57, 85, 113, 141, and 169/End of Treatment (EOT)

Prior to study drug administration (pre-dose procedures):

- directed physical examination;
- adverse event assessment;
- interim medication history;
- vital signs (temperature, respiratory rate, blood pressure and pulse);

- Chem-20, CBC, UA;
- measurement of SLE activity (SLEDAI-2K, BILAG-2004, PGA);
- measurement of cutaneous disease activity (CLASI);
- tender and swollen joint count;
- photographs of cutaneous disease activity (Days 85 and 169 only);
- FACIT fatigue index (subject completes form) (Days 85 and 169 only);
- serum for study drug concentration (Days 29, 85, and 169 only);
- serum for protein analysis (Day 85 and 169 only);
- serum for RNase activity (Days 29, 85, and 169 only);
- whole blood for gene expression profile (Days 29, 85, and 169 only);
- serum for autoantibody profile (Ro-52/60, La, Sm, SmRNP, U1 RNP A/68, dsDNA) C3 and C4 (local or central laboratory);
- serum for assessment of anti-RSLV-132 antibodies (Days 29 and 85 only);
- **after completion of above assessments:**
  - study drug administration (except Day 169)

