## 12.6 End of Study Day 215 Evaluations

The following procedures will be performed on Day 215:

- directed physical examination;
- pregnancy test (serum).
- adverse event assessment;
- interim medication history;
- vital signs (including temperature, respiratory rate, and seated blood pressure and pulse);
- clinical laboratory evaluations (Chem-20, CBC, and UA);
- serum for study drug concentration;
- serum for measurement of RNase activity;
- whole blood for gene expression profile;
- serum for assessment of antibodies to RSLV-132;

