## **12.14 Anti-Drug Antibodies**

Serum will be analyzed by ICON for the presence of anti-RSLV 132 antibodies using a validated immunoassay. Each positive serum sample will be evaluated for ADA specificity by repeating the immunoassay in the presence of an excess of RSLV-132. Confirmed positive, specific serum samples will be titered by serial dilution and a numerical titer will be assigned.

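### SAP 10.3 has no category for an antibody-negative sample that contains drug, so active-arm immunogenicity may be understated, depending on an assay drug tolerance that the documents do not give

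*SAP*

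**What the plan says.** Immunogenicity is a secondary objective (Protocol 4.2, SAP 2.1.2), and SAP 10.3 evaluates it among the safety endpoints. The planned output is that "the number and percent of positive and negative results will be summarized descriptively by treatment groups on the SAS", with percentages taken over subjects who have a sample at the visit.

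After Baseline, antibody serum is drawn on Day 15 (Protocol 12.4), on Days 29 and 85 (Protocol 12.5: "serum for assessment of anti-RSLV-132 antibodies (Days 29 and 85 only") and at the end-of-study visit on Day 215 (Protocol 12.6). At the three dosing visits it is drawn before the infusion. Infusions are given on Days "1, 8, 15, 29, 43, 57, 71, 85, 99, 113, 127, 141, and 155" (Protocol 5.1).

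On the assay, Protocol 12.14 states: "Each positive serum sample will be evaluated for ADA specificity by repeating the immunoassay in the presence of an excess of RSLV-132". SAP 10.3 repeats this step. Both documents call the assay validated; neither gives its drug tolerance.

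On elimination, Protocol 3.4.1 reports: "The serum half-life of the drug was measured to be approximately 16 days".

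Drug concentration is sampled on Days 29, 85 and 215, the same visits as antibody, but not on Day 15. SAP 11 summarizes concentrations only if they are available and does not link them to antibody status.

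**The concern.** A specificity step that adds excess drug works because free drug competes for the antibody. Active-arm serum drawn during dosing already contains drug when it is screened. If the assay does not tolerate that concentration, a subject with antibodies can screen negative, and SAP 10.3 then counts the sample with the true negatives.

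Placebo serum contains no drug, so an error of this kind can occur only in the active arm and only towards too few positives. A zero or low percentage on Days 15, 29 and 85 could then be read as absence of immunogenicity when the assay may have been unable to detect it. Day 85 matters most: the objective names Days 85 and 169, and no antibody sample is scheduled on Day 169.

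**Working it through.** The plan gives no antibody rate, residual drug level or drug tolerance, so there is no figure of its own to reproduce. The dose list does count to the stated 13 infusions.

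**Step 1: drug present at each antibody sample.** Inputs are the dosing days d (Protocol 5.1), the sampling days t (Protocol 12.4 to 12.6) and the half-life h = 16 days (Protocol 3.4.1). Assume one compartment, full adherence and nominal visit days. In units of the level just after one 10 mg/kg dose:

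L(t) = sum over earlier doses of 2^(−(t − d)/h)

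- Day 15 (doses 14 and 7 days earlier): 0.545 + 0.738 = 1.28
- Day 29 (28, 21 and 14 days earlier): 0.297 + 0.403 + 0.545 = 1.25
- Day 85 (84, 77, 70, 56, 42, 28 and 14 days earlier): 0.026 + 0.036 + 0.048 + 0.088 + 0.162 + 0.297 + 0.545 = 1.20
- Day 215: the level just after the Day 155 infusion is 2.199. Sixty days is 60/16 = 3.75 half-lives, so 2.199 × 2^(−3.75) = 2.199 × 0.0743 = 0.16

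Day 215 thus carries 7.4% of the level just after the last infusion, or 9.2% to 6.0% across the ±5-day window (55 to 65 days after Day 155).

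**Step 2: sensitivity to the half-life.** The 16 days come from single doses in healthy volunteers. The range of 12 to 20 days is an assumption.

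| Sample | h = 12 | h = 16 | h = 20 |
|---|---|---|---|
| Day 15 | 1.11 | 1.28 | 1.40 |
| Day 29 | 0.94 | 1.25 | 1.48 |
| Day 85 | 0.81 | 1.20 | 1.58 |
| Day 215 | 0.06 | 0.16 | 0.33 |

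Pre-dose sampling therefore does not clear the drug at the three dosing visits. Day 215 is clearly the lowest-drug sample throughout.

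**Step 3: what masking could do to the table.** With 2:1 allocation of about 50, the active arm has about 50 × 2/3 = 33 subjects. Assume a true antibody rate of 10%, and let s be the assay's sensitivity in the presence of drug. Neither value is in the documents. Expected positives are 33 × 0.10 × s, and the chance of seeing none is (1 − 0.10s)^33.

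| s | Expected positives | Chance of none |
|---|---|---|
| 100% | 3.3 | 3% |
| 50% | 1.65 | 18% |
| 25% | 0.83 | 43% |

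The first row is the fully drug-tolerant assay, where nothing is lost. The table shows how the result depends on s; it does not estimate what will happen.

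**The case against.** A reader might infer that antibody is in fact being masked and that the plan does understate immunogenicity. The documents do not support that. Everything turns on drug tolerance, and validation of the assay may have covered it. The documents also give no assay format, dilution or pretreatment, so the levels in the working cannot be compared with any threshold. This objection stands, and it limits the point to a possibility.

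A reader might also blame the excess-drug step for lost positives. It is run only on samples that have already screened positive. It shows that drug can compete; any masking of serum antibody would arise earlier, at screening.

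Day 215 should not be grouped with the on-treatment samples. It has far less drug and already has its own row and denominator under SAP 10.3. That is correct, and it is a reason to present it separately.

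Finally, the analysis is descriptive, in a proof-of-concept trial without formal hypothesis testing. That lowers the stakes. It does not make an uninterpretable negative interpretable. Nor does the absence of confirmed positives in the earlier 113-day study (Protocol 3.4.2), which says nothing about drug tolerance.

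**Conclusion.** The point holds in a limited form. Three of the four post-baseline antibody samples in the active arm are drawn with about 1.2 to 1.3 single-dose levels of drug in the serum (about 0.8 to 1.6 on Day 85 for assumed half-lives of 12 to 20 days). The fourth is drawn with about 0.16. SAP 10.3 calls every sample positive or negative and ignores the paired concentration. On-treatment negatives therefore cannot be interpreted from the planned table alone, and immunogenicity may be understated in the active arm.

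Whether it is, and by how much, cannot be determined without the assay's drug tolerance. The level estimates assume mono-exponential decay, full adherence and a healthy-volunteer half-life applied to subjects with SLE.

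**What to change.** In SAP 10.3:

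1. Cite the assay's drug tolerance from the validation report.
2. On Days 29, 85 and 215, class an antibody-negative sample as inconclusive when its paired RSLV-132 concentration exceeds that tolerance.
3. Flag active-arm negatives on Day 15 as having no paired concentration.
4. Report counts and percentages of positive, negative and inconclusive results, with all sampled subjects in the denominator.
5. Show Day 215 separately as the post-baseline time point with the least drug.

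The denominator should not be cut to positives plus conclusive negatives. If every active-arm negative at a visit were inconclusive, that denominator would hold positives only: one positive among 33 subjects would be reported as 1/1 = 100% instead of 1/33 = 3%, and no positives would give 0/0.

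The cost is SAP wording and a merge of concentration data with antibody data. SAP 11 would also have to treat the concentrations as a needed input, where it now summarizes them only if available. No new samples are required. The downside is that fewer on-treatment samples can be called negative. If the tolerance exceeds every measured level, no sample on Days 29, 85 or 215 changes category, and the table gains a stated basis for its negatives.

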2.1.2. Secondary Objectives

The secondary objectives of the study are:

At Days 85 and 169:

- to assess disease activity using Systemic Lupus Erythematosus Disease Activity Index SLENA (safety of estrogens in lupus erythematosus national assessment) Modification (SLEDAI-2K), British Isles Lupus Activity Group (BILAG-2004) and physician's global assessment (PGA);
- to evaluate the immunogenicity of RSLV-132 in subjects with systemic lupus erythematosus;
- to assess improvement in tender or swollen joint count;
- to assess improvement in patient reported outcomes using the Functional Assessment of Chronic Illness Therapy (FACIT)-Fatigue scale;
- to assess the proportion of subjects achieving a 50% improvement in CLASI activity score.

At Day 169:

- to assess the ability of subjects to reduce oral steroids at Day 169 relative to Day 85;
- to evaluate the safety and tolerability of 22 weeks of RSLV-132 exposure.

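### SAP 10.3 summarises anti-drug antibodies only visit by visit, so it neither separates new from pre-existing positivity within a subject nor gives the proportion ever positive after baseline.

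*SAP*

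**What the plan says.** Immunogenicity is a secondary objective in both documents. SAP 2.1.2 words it as "to evaluate the immunogenicity of RSLV-132 in subjects with systemic lupus erythematosus", under the heading for Days 85 and 169; Protocol 4.2 sets the same time points. Protocol 11.3 lists the presence of antibodies among the measures to be compared between arms.

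The analysis is in SAP 10.3: "The immunogenicity of RSLV-132 as measured by the presence of RSLV-132 antibodies will be evaluated as part of the safety endpoints". The method is: "To assess immunogenicity, the number and percent of positive and negative results will be summarized descriptively by treatment groups on the SAS" (SAS here is the Safety Analysis Set). The denominator rule follows: "The percentages will be calculated based on the number of subjects in each treatment group with samples available at each visit".

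The data collected go further than that summary. Protocol 12.3 lists "serum for assessment of antibodies to RSLV-132" among the Day 1 pre-dose procedures. Later samples fall on Day 15 (Protocol 12.4), Days 29 and 85 (12.5) and Day 215 (12.6). Protocol 12.14 adds: "Confirmed positive, specific serum samples will be titered by serial dilution and a numerical titer will be assigned". Neither document defines treatment-induced or boosted ADA, a shift from baseline, an any-time post-baseline rate, or a summary of titres.

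**The concern.** A by-visit percentage is a prevalence among those sampled that day. The usual questions about immunogenicity are how many subjects became positive after exposure, and how strongly. Separate visit rows cannot answer the first, for two reasons. A subject who was positive before dosing stays in the numerator of later rows, unseparated from subjects who turned positive on treatment. And one positive in each of several rows may be one person or several. The second question needs the titres, which are assigned but appear in no planned table.

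At stake is whether the report on a named secondary objective, which the SAP also treats as a safety endpoint, can state a per-subject rate under a rule fixed in advance.

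**Working it through.** The documents give no expected ADA rate, so there is no planned figure to reproduce. The check asks what the planned table can and cannot determine. Positive counts below are assumed, and every subject is taken to have every sample.

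**Inputs.**
- About 50 subjects at 2:1 (SAP 2.3.1): 50 × 2/3 = 33.3 and 50 × 1/3 = 16.7, so about 33 active and 17 placebo.
- One baseline sample (Day 1) and four post-baseline samples (Days 15, 29, 85, 215).

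**Ever positive after baseline.** If each of the four post-baseline rows shows k positives, the number of subjects ever positive lies between k (the same subjects each time) and 4k (different subjects each time).

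**New positivity.** If the Day 1 row shows no positives, every later positive is new and the ever-positive range applies. If the Day 1 row also shows k positives, there are 33 − k baseline-negative subjects. The number newly positive then runs from 0 (the same k subjects throughout) to 4k.

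| k per visit | Each row | Ever positive after baseline | New positivity if Day 1 also shows k |
|---|---|---|---|
| 1 | 1/33 = 3.0% | 1/33 to 4/33 (3.0% to 12.1%) | 0/32 to 4/32 (0% to 12.5%) |
| 2 | 2/33 = 6.1% | 2/33 to 8/33 (6.1% to 24.2%) | 0/31 to 8/31 (0% to 25.8%) |
| 3 | 3/33 = 9.1% | 3/33 to 12/33 (9.1% to 36.4%) | 0/30 to 12/30 (0% to 40.0%) |

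In the placebo arm, one persistently reactive subject shows as 1/17 = 5.9% in every row.

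**Would a baseline positive occur at all?** With pre-existing prevalence p, the chance of at least one among 33 is 1 − (1 − p)^33. For assumed p of 1%, 3%, 5% and 10% this is 0.28, 0.63, 0.82 and 0.97.

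**Earlier data.** Protocol 3.4.1 reports no positives in 132-01 and Protocol 3.4.2 no confirmed positives in 132-02. The 132-02 active arm had 24 subjects (5 subjects given as 20.8%; 5/24 = 20.8%). Zero of 24 leaves a one-sided 95% upper limit of 1 − 0.05^(1/24) = 11.7%.

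**The SAP's own practice elsewhere.** Adverse events are defined relative to first dose, and each subject is counted once per term (10.1). Autoantibodies have shifts from baseline (9.3.1). Physical examination has new, unchanged, worsened and improved categories (10.2.4). ADA has no equivalent.

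**Sampling gap.** From Day 85 to Day 215 is 130 days without an ADA sample. The Day 85 sample is pre-dose, so six of the 13 infusions (Days 85, 99, 113, 127, 141, 155) fall in that interval. Protocol 12.5, Protocol Appendix A and SAP Table 1 show no ADA sample on Day 169, although the objective names that day.

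**The case against.** The strongest reply is that the SAP does what the protocol asks. Protocol 11.3 defines the measure as presence of antibodies, and SAP 10.3 reports presence by arm. That stands: the SAP does not contradict its protocol, and the objective's wording does not say that induction is the target.

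Two stronger readings are tempting and should be resisted:
- **That pre-existing antibody is counted as drug-induced.** The SAP never applies that label. A pre-existing reactor would show in the Day 1 row as well as later ones, and the placebo arm shows background reactivity alongside.
- **That the baseline sample goes unused.** Day 1 is a scheduled ADA visit and should have its own row. What is missing is the within-subject link. Only the titres are wholly absent from the planned summaries.

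Other points also carry weight. SAP section 5 provides for listings of collected data, so with about 33 active subjects each history can be traced by hand. The rows bound the cumulative rate. Subjects who stop treatment early are still sought for the End of Study visit (Protocol 6.4), which includes an ADA sample, so loss from later denominators is partial. The study is descriptive, without formal testing. And if few or no subjects turn positive, the by-visit and per-subject tables will say nearly the same thing.

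The core of the point remains. One positive on Day 1 and one on Day 85 may be one person or two, and the rows cannot say which. Deriving the answer from listings leaves the classification rule, especially what titre rise counts, to be chosen after results are known.

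**Conclusion.** The point holds as a gap in the planned summaries, not as an error in the data or a departure from the protocol. By-visit rows do not identify either per-subject quantity. With one positive per post-baseline visit among 33 active subjects, the same 3.0% rows fit an ever-positive incidence of 3.0% to 12.1%. They also fit zero new positivity if one subject was positive throughout, Day 1 included.

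Those counts are illustrations under complete sampling; the upper end requires a different subject at each visit. If the Day 1 row shows no positives, the confusion of old with new disappears and only the uncertainty about how many subjects were ever positive remains. The earlier studies suggest that the practical effect may be small, though 0 of 24 does not rule out a rate of up to about 11.7%. The change is worth making because it is cheap and matches how the SAP treats its other baseline-referenced data.

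**What to change.** Keep the by-visit table. Add one descriptive per-subject table by arm on the Safety Analysis Set, showing:

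- **(a)** baseline ADA prevalence;
- **(b)** treatment-induced ADA: confirmed negative on Day 1 and confirmed positive at any later sample, with baseline-negative subjects who have at least one post-baseline sample as the denominator;
- **(c)** peak titre of positive subjects, with baseline and peak titres of baseline-positive subjects shown separately.

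If boosted ADA is to be reported as a category, fix the titre-rise threshold before unblinding, from the assay's validated variability. The documents give no figure from which to set it.

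State that no ADA sample falls between Day 85 and Day 215, so even the any-time rate can miss transient positives in that interval. Reconcile the Day 169 time point in Protocol 4.2 and SAP 2.1.2 with the sampling schedule.

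The cost is one definition, one table and a sentence of limitation, all from data already collected. No test is added.
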